4.3 Tertiary Objectives

1. To evaluate the effects of LCZ696 compared to valsartan over 24 weeks on:
 - a. Time to death
 - b. Time to first HF hospitalization
 - c. Time to death or first HF hospitalization
 - d. Total HF hospitalizations
 - e. Number of subjects on continuous inotropic therapy ≥ 7 days after discharge from the index hospitalization.
 - f. Number of subjects, listed for transplant (status 1A, 1B or 1-4), transplanted or implanted with an LVAD
 - g. Change in eGFR and cystatin C levels compared to baseline. Renal function will be assessed at baseline, 4, 8, 12, and 24 weeks.
 - h. Number of subjects with unanticipated use of IV diuretics (outpatient, ER or inpatient)

- i. Change in AUC in the Kansas City Cardiomyopathy Questionnaire (KCCQ) at 4, 12, and 24 weeks compared to baseline
- j. The change in the AUC for the ratio of NT-proBNP/BNP from baseline to 2, 4, 8, 12, and 24 weeks

4.4 Exploratory Objective

Modified Clinical Composite endpoint including Death, LVAD or Heart Transplant (including Listing status of 1A, 1B or 1-4), Multiple HF Hospital Admissions, Single HF admission

5 BACKGROUND

Patients with advanced HFrEF have extremely high morbidity and mortality with 1 year outcomes of death and hospitalization of approximately 50%.^{1,3} Although ACEI/ARBs, beta-blockers and spironolactone are currently approved for use in patients with advanced heart failure (NYHA class IV), the overall morbidity and mortality in this class of patients remains unacceptably high. For the most advanced heart failure patients, the evidence base for medical treatment is limited with consensus guidelines recommending consideration for either cardiac transplant or ventricular assist device, or palliative care.³

Recently, a new class of therapeutic agent, a dual angiotensin receptor blocker (ARB) angiotensin receptor blocker neprilysin inhibitor (ARNIs) has been approved for use in patients with NYHA class II-IV heart failure. LCZ696 is an ARNI consisting of the neprilysin inhibitor sacubitril (AHU377) and the ARB valsartan. Neprilysin (NEP) is a membrane bound enzyme (peptidase) that can be “shed” and circulated in a biologically active form in the circulation. NEP catalyzes the degradation of a number of endogenous peptides, including natriuretic peptides, angiotensin II, bradykinin, substance and amyloid β peptide, which has been implicated in Alzheimer’s disease. In heart failure, NEP inhibition leads to increased circulating levels of these vasoactive peptides, thereby offsetting the deleterious effects of neurohormonal over activation, that contribute to peripheral vasoconstriction, sodium retention, and maladaptive left ventricular remodeling. In small clinical trials in patients with heart failure with a preserved ejection fraction or who had hypertension, LCZ696 had hemodynamic and neurohormonal effects that were greater than those of an ARB alone.

6 PRELIMINARY STUDIES (STUDY RATIONALE)

The PARADIGM-HF trial showed that LCZ696 improved morbidity and mortality in patients with chronic HFrEF in comparison to enalapril.² In PARADIGM-HF, 8442 patients with class II, III, or IV heart failure and an ejection fraction of 40% or less were randomized to receive LCZ696 (at a dose of 200 mg twice daily) or enalapril (at a dose of 10 mg twice daily), in addition to evidence

based medical therapy for heart failure. The primary outcome variable for the trial was a composite of death from cardiovascular causes or hospitalization for heart failure. The trial was stopped early for benefit in the LCZ696 treatment arm. At the time of study closure, the primary outcome had occurred in 914 patients (21.8%) in the LCZ696 group and 1117 patients (26.5%) in the enalapril treatment arm (HR 0.80; 95% CI, 0.73 - 0.87; P < 0.001). Moreover, there was a significant overall mortality benefit for LCZ696 when compared to enalapril (HR 0.84; 95% CI, 0.76 - 93; P <0.001). Despite the striking clinical benefits for LCZ696 in the PARADIGM-HF trial, limited experience with advanced heart failure patients was gained from patients enrolled in the trial. In the PARADIGM-HF trial a total of 33 patients (0.8%) with class IV heart failure were randomized to the treatment arm with LCZ696. Moreover, a recent study by Vodovar in patients with acute decompensated heart failure suggests that high circulating levels of endogenous B-type natriuretic peptide (BNP) and proBNP are capable of inhibiting the enzymatic activity of circulating NEP,⁴ raising the possibility that the NEP inhibition may be less effective in patients with more advanced heart failure.

Because the information on the effects of sacubitril/valsartan in patients with NYHA class IV heart failure is limited, the updated 2016 ACC/AHA/HFSA guidelines for the treatment of heart failure do not endorse the use of sacubitril/valsartan in patients with NYHA class IV heart failure⁵

Accordingly, additional experience is needed on the use of, and outcomes with LCZ696 in patients unable to tolerate target doses of ACEI/ARB.

7 STUDY DESIGN

7.1 Screening / Baseline

Subjects will have an initial screening evaluation, including baseline laboratory tests as well as an assessment of LV ejection fraction, at which time preliminary subject eligibility will be determined. The LV ejection fraction may have been obtained within the prior 12 months by 2-D echocardiogram, LV angiogram or radionuclide scintigraphy. Willing subjects meeting entry criteria will be consented. Those who meet all entry criteria and are interested in study participation will be enrolled.

Enrolled subjects will complete baseline assessments and undergo a run-in period of 3-7 days with LCZ696 50 mg (equivalent to Entresto™ 24/26 mg) po BID prior to randomization. For subjects taking an ACEI, the ACEI will be withheld for ≥ 36 hours prior to first dose of LCZ696.

7.2 Randomization Phase

This will be a 2-arm randomized, double-blind, controlled trial with an active treatment arm (valsartan).

Subjects who tolerate the run-in period with LCZ696 will be randomized 1:1 to LCZ696 or valsartan. Subjects will be randomized using procedures determined by the Coordinating Center

(CC) to one of the two treatment groups.

7.3 Study Intervention Phase

Study treatment will be titrated to the target dose of 200 mg LCZ696 (equivalent to Entresto™ 97/103 mg) as two 100 mg LCZ696 and 2 placebo tablets po BID or valsartan 160 mg (two 80 mg valsartan and 2 placebo tablets) po BID.* Randomized subjects will receive the first dose of study drug as follows:

[figure not shown]
- For subjects not previously taking ACEI or ARB, previously taking ACEI or ARB at a low dose*, or subjects who have an eGFR < 30 mL/min/1.73m², the starting dose of valsartan will be 40 mg po BID and the starting dose of LCZ696 will be 50 mg po BID.
- For subjects taking an ARB at greater than low dose†, the starting dose of valsartan will be 80 mg po BID and the starting dose of LCZ696 will be 100 mg po BID.
- For subjects taking an ACEI at greater than low dose†, the ACEI will be withheld for ≥ 36 hours prior to randomization. The starting dose of valsartan will be 80 mg po BID and the starting dose of LCZ696 will be 100 mg po BID.

* Per package insert, the valsartan compounded in Entresto™ is more bioavailable than the valsartan in other marketed formulations. The dose equivalence for valsartan compounded in Entresto™ compared to valsartan prepared alone (Entresto™ dose = marketed valsartan dose) is as follows: 26 mg=40 mg, 51 mg=80 mg, 103 mg=160 mg.

† Low dose is defined as 24 hour dose of ≤ 10 mg lisinopril, ≤ 5 mg ramipril, ≤ 50 mg losartan, ≤ 10 mg olmesartan, or other dose equivalent.

Dose adjustments will be performed every 2 weeks by doubling the dose of LCZ696 or valsartan up to the target maximum dose. The doses of LCZ696 are 50 mg (one 50 mg active and 1 placebo tablet), 100 mg (one 100 mg active and 1 placebo tablet) and 200 mg (two 100 mg active and 2 placebo tablets). These doses are equivalent to 24/26 mg, 49/51 mg, and 97/103 mg commercial Entresto™, respectively. The doses of valsartan are 40mg (one 40 mg active and 1 placebo tablet), 80 mg (one 80 mg active and 1 placebo tablet), and 160 mg (two 80 mg active and 2 placebo tablets). The criteria for doubling the dose will be based on systolic blood pressure (a SBP > 90 mmHg is required for up titration), changes in renal function (maximum serum creatinine of 2.0 mg/dL), and the absence of symptoms of hypotension. For those not tolerating the current dose of study drug, the dose will be down-titrated to the previous tolerated dose. Subjects will return to clinic for follow-up visits at 2, 4, 8, 12, 24 and 26 weeks after randomization.

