10.4 Dosing Guidelines

The study will begin with a 3-7 day run-in period in which all subjects will be administered LCZ696 50 mg po BID. For those subjects taking ACEI prior to the run-in period, the first dose of LCZ696 will be withheld ≥ 36 hours after last ACEI dose. After stopping LCZ696, a 36 hour washout period is required before resuming an ACEI.

Subjects tolerating the LCZ696 in the run-in period will be randomized to either LCZ696 or valsartan. Doses will be assigned in the following fashion:

If previously taking no ACEI/ARB, low-dose ACEI/ARB[†], or eGFR < 30 ml/min/1.73m², ensure ACEI has been discontinued and the last dose was ≥ 36 hours ago, then

- LCZ696 50 mg plus placebo po BID or valsartan 40 mg plus placebo po BID

If previously taking greater than low dose ARB[†]

- LCZ696 100 mg plus placebo po BID or valsartan 80 mg plus placebo po BID*

If previously taking greater than low dose ACEI[†], ensure ACEI was discontinued and the last dose was \geq 36 hours ago, then

- LCZ696 100 mg plus placebo po BID or valsartan 80 mg plus placebo po BID*

* At Investigator discretion, study drug may be started at the low dose (LCZ696/placebo 50 mg po BID or valsartan/placebo 40 mg po BID) if there are any concerns regarding tolerability at the 100 mg / 80 mg dose.

Two weeks after randomization, upward dose titration will occur among subjects tolerating their current dose (SBP > 90 mmHg, creatinine (Cr) \leq 2.0 mg/dL, and no symptoms of hypotension). This will consist of doubling the dose up to a maximum dose LCZ696 200 mg po BID (two 100 mg tablets plus 2 placebo tablets po BID) or valsartan 160 mg po BID (two 80 mg tablets and 2 placebo tablets po BID). For those not tolerating the current dose of study drug, the dose will be down-titrated to the previous tolerated dose.

Two weeks after the prior dose titration visit and four weeks after randomization, further dose titration will occur among subjects tolerating their current dose (SBP > 90 mmHg, Cr \leq 2.0 mg/dL, and no symptoms of hypotension). This will consist of doubling the dose up to a maximum dose LCZ696 200 mg po BID or valsartan 160 mg po BID. For those not tolerating the current dose of study drug, the dose will be down-titrated to the previous tolerated dose. The total duration of study drug treatment will be 24 weeks.

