12 VISIT SCHEDULE AND ASSESSMENTS

12.1 Baseline Evaluation and Randomization Visit

A complete schedule of assessments throughout the study is given in Appendix A.

Screening/Study Visit 0 (Enrollment)

This visit will include the screening and informed consent process followed by a baseline assessment including:

- Medical history including etiology and duration of HF, documented history of HF visits within 6 months
 - Confirmation of ejection fraction $\leq 35\%$ within the last 12 months
 - Physical examination including height and weight
 - NYHA class assessment
 - Review of medications
 - KCCQ quality of life questionnaire
 - Local laboratory testing, including the following:
 - Sodium
 - Potassium
 - Chloride
 - CO₂/bicarbonate
 - Total calcium
 - Magnesium
 - Blood Urea Nitrogen (BUN)
 - Creatinine
- For Screening/Study Visit 0 only - Standard of care labs are acceptable, using results within 24 hours prior for hospitalized patients and within 7 days prior for outpatients.
- Serum pregnancy test on all women of childbearing potential
 - Discontinue ACEI 36 hours prior to the start of the run-in phase, if applicable

Study Visit 1 (Begin run-in phase)

Visit 1 should take place within 7 days of the screening visit. This visit will begin the 3-7 day run-in period. All subjects will be administered LCZ696 50 mg po BID. For those subjects taking ACEI prior to the run-in period, ensure that the ACEI has been discontinued and last dose of ACEI was ≥ 36 hours prior to the first dose of LCZ696.

Assessments at this visit include:

- Interim history
- Review of medications
- Physical examination with NYHA class assessment
- Local laboratory testing (creatinine, BUN, electrolytes – see visit 0 for labs to be collected)
- Adverse event monitoring.

For subjects who are stable and for whom lab results have been reviewed, the Screening Visit and Visit 1 may be combined at the investigator's discretion as long as the investigator ensures the 1st dose of LCZ696 is ≥ 36 hours after last ACEI dose (if applicable).

Study Visit 2 (End run-in phase / Begin Randomization)

At this visit, those subjects tolerating the LCZ696 in the run-in period will be randomized to either LCZ696 or valsartan. Randomization should occur immediately following the end of the run-in phase. If the subject cannot return to the clinic within 7 days of starting the run-in phase,

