the subject should continue to take LCZ696 po BID until the randomization visit and site personnel should notify the CC. Subjects who fail the open-label run-in phase should receive a follow-up contact approximately 2 weeks after the last dose of study drug.

Doses will be assigned in the following fashion:

If previously taking no ACEI/ARB, low-dose ACEI/ARB[†], or eGFR < 30 ml/min/1.73m² ensure ACEI has been discontinued and the last dose of ACEI was ≥36 hours ago, then

- LCZ696 50 mg po plus placebo BID or valsartan 40 mg po BID plus placebo

If previously taking greater than low dose ARB[†]

- LCZ696 100 mg po plus placebo BID or valsartan 80 mg po BID plus placebo*

If previously taking greater than low dose ACEI[†], ensure ACEI has been discontinued and the last dose of ACEI was ≥ 36 hours ago, then

- LCZ696 100 mg po plus placebo BID or valsartan 80 mg po BID plus placebo*

† Low dose is defined as 24 hour dose of ≤ 10 mg lisinopril, ≤ 5 mg Ramipril, ≤ 50 mg Losartan, ≤ 10 mg Olmesartan, or other dose equivalent.

* At Investigator discretion, study drug may be started at the low dose (LCZ696/placebo 50 mg po BID or valsartan/placebo 40 mg po BID) if there are any concerns regarding tolerability at the 100 mg / 80 mg dose.)

Study drug will be supplied in kits (containing both active and placebo tablets) and will be administered as follows:

- 50 mg LCZ696 / 40 mg valsartan = one low-dose active tablet and one low-dose placebo tablet po BID
- 100 mg LCZ696 / 80 mg valsartan = one high-dose active tablet and one high-dose placebo tablet po BID
- 200 mg LCZ696 / 160 mg valsartan = two high-dose active tablets and two high-dose placebo tablets po BID

Assessments at this visit include:

- Interim history
- Review of medications
- Physical examination with NYHA class assessment
- Routine laboratory testing (creatinine, BUN, electrolytes – see visit 0 for labs to be collected)
- Core laboratory testing (Cystatin C, BNP, NT-proBNP)
- Adverse event monitoring

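### Section 7.3 counts the 36-hour ACEI washout back from randomization, and only above low dose, while 7.1 and the run-in instructions count it back from the first LCZ696 dose for any ACEI user; the passages need reconciling

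*Protocol*

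**What the plan says.** Protocol section 7.3 assigns the first randomized dose. Its bullet for higher-dose ACEI users says: "For subjects taking an ACEI at greater than low dose†, the ACEI will be withheld for ≥ 36 hours prior to randomization". Its bullet for subjects with no prior ACEI or ARB, a low prior dose, or eGFR below 30 gives no washout.

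Other places use a different reference point:

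- Section 7.1, for any subject taking an ACEI: "the ACEI will be withheld for ≥ 36 hours prior to first dose of LCZ696".
- Section 10.4, run-in paragraph: "the first dose of LCZ696 will be withheld ≥ 36 hours after last ACEI dose".
- Section 12.1, Visit 0: "Discontinue ACEI 36 hours prior to the start of the run-in phase, if applicable". Visit 1 again ties the interval to the first LCZ696 dose.
- Section 8 and the Appendix A footnote repeat the first-dose reference point for the case where screening and Visit 1 are combined.

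At Visit 2, the randomization visit, section 12.1 tells sites to "ensure ACEI has been discontinued and the last dose of ACEI was ≥36 hours ago". That line covers the low-dose group. An equivalent line covers higher-dose ACEI users, and section 10.4 has both.

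On the run-in, section 10.4 says: "The study will begin with a 3-7 day run-in period in which all subjects will be administered LCZ696 50 mg po BID". If a subject cannot return within 7 days, section 12.1 adds that "the subject should continue to take LCZ696 po BID until the randomization visit". Section 10.10 bars ACE inhibitors for the duration of the study. SAP section 1.2 repeats the starting doses without any washout rule.

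**The concern.** Randomization is not the first exposure to LCZ696. A washout counted back from randomization therefore ends days after LCZ696 has started, and the section 7.3 bullet reads as though there were no run-in. It also names a narrower group, higher-dose ACEI users, than section 7.1 or the Visit 2 checks do.

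A site that takes its ACEI instruction from section 7.3 has a weaker rule than one that takes it from section 7.1. The Visit 2 checks use the same 36-hour figure counted from that visit, so this part of the check does not test whether the earlier washout was met. The protocol states the interval in many places and lists angioedema as an event of interest, so it evidently treats the separation as important. Tolerating the run-in is also the condition for being randomized. ACEI use during that period would make hypotension or a renal change harder to attribute. The documents do not allow either consequence to be sized.

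**Working it through.** The plan states no figure to reproduce. The check is a timeline.

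**Inputs**

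- Washout length: 36 h (sections 7.1, 7.3, 10.4, 12.1).
- Run-in length: 3 to 7 days, from section 7.1 ("undergo a run-in period of 3-7 days with LCZ696 50 mg") and section 10.4. In hours, 3 × 24 = 72 and 7 × 24 = 168.
- Set the first run-in dose of LCZ696 at t = 0. Randomization is then at t = R, with R between 72 h and 168 h.

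**Latest last ACEI dose that each rule accepts**

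| Rule | Formula | 3-day run-in | 7-day run-in |
|---|---|---|---|
| 7.1: back from first LCZ696 dose | t = −36 h | −36 h | −36 h |
| 7.3 read alone: back from randomization | t = R − 36 h | 72 − 36 = 36 h | 168 − 36 = 132 h |

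**Time off ACEI at randomization**

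- Under 7.1: at least R + 36, that is 72 + 36 = 108 h to 168 + 36 = 204 h.
- Under 7.3 read alone: at least 36 h.

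Meeting 7.1 therefore always meets 7.3, but not the reverse. The two limits differ by the length of the run-in, 72 to 168 h.

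**What the 36-hour element at Visit 2 can tell apart**

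| Last ACEI dose before randomization (3-day run-in; 7-day run-in) | Meets 7.1? | Passes the 36-hour element? |
|---|---|---|
| 108 h or more; 204 h or more | Yes | Yes |
| 72 to under 108 h; 168 to under 204 h (before LCZ696, but washout incomplete) | No | Yes |
| 36 to under 72 h; 36 to under 168 h (during run-in) | No | Yes |
| Under 36 h | No | No |

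The element fails only subjects in the last row. If the run-in exceeds 7 days, which section 12.1 allows, each extra day adds 24 h to the upper limits.

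**Subjects covered**

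| Place | ACEI users covered |
|---|---|
| 7.1; 10.4 run-in paragraph; 12.1 Visits 0 and 1 | Any dose |
| 10.4 and 12.1, Visit 2 lines | Low and higher dose |
| 7.3 | Higher dose only |

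**The case against.** The strongest reply is that section 7.3 is never applied alone. Every subject first comes under section 7.1, the Visit 0 instruction to stop the ACEI, and the Visit 1 check against the first LCZ696 dose. Section 10.10 then bars ACE inhibitors throughout. Both rules can always be followed together, so 7.3 is at worst a redundant lower bound in a section about starting doses. The Visit 2 text has two parts: it asks that the ACEI has been stopped as well as that 36 hours have passed. Visit 2 also includes an interim history and a medication review. All of this stands, and it rules out several stronger readings:

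- A reader might infer that the protocol permits ACEI use alongside LCZ696. It does not: sections 7.1, 10.4, 10.10 and Visits 0 and 1 all exclude it.
- A reader might infer that Visit 2 cannot detect overlap. Only the 36-hour element is blind to it; the medication review could reveal it.
- A reader might infer that low-dose ACEI users have no washout. Section 7.1 and Visits 0 and 1 set no dose limit.
- A reader might infer a quantified angioedema risk. Section 11.6 compares LCZ696 with enalapril and gives no figure for the two classes taken together.

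Some text is also unavailable: a figure directly above the section 7.3 bullets is not shown, and the section 8 flow-diagram text for the earlier visits is not in the copy read. Clarifying wording there cannot be excluded.

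What the reply does not remove is that an operative safety instruction names a reference point and a set of subjects that differ from those elsewhere in the same protocol.

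**Conclusion.** The inconsistency is real and minor. Read alone, section 7.3 would be met by ACEI use continuing until 36 h after the first LCZ696 dose with a 3-day run-in, or 132 h with a 7-day run-in. Section 7.1 allows none and implies at least 108 to 204 h off ACEI at randomization. These windows assume the planned 3 to 7 day run-in and a site that follows 7.3 in place of the other instructions. They do not describe what the whole protocol allows, and no frequency of such use can be derived from the documents. This is a wording fault and not a design choice. Sample size, power, alpha and the analyses are unaffected.

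**What to change.** Reconcile section 7.3 and the Visit 2 wording in sections 10.4 and 12.1 with sections 7.1 and 10.10, the Visit 0 and Visit 1 instructions, section 8 and Appendix A. The washout should have one reference point and one defined set of subjects wherever it appears. Word the Visit 2 confirmation so that it tests the reconciled rule, using the medication review already scheduled there. The clinical content of the rule is for the sponsor to set.

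The cost is wording in three sections and one item in an existing review. No visit, sample or analysis changes.

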8 STUDY FLOW DIAGRAM

The Screening visit and Visit 1 may be combined at the investigator's discretion for subjects who are stable, and for whom lab results have been reviewed as long as the investigator ensures the 1st dose of LCZ696 is \geq 36 hours after last ACEI dose (if applicable). If not combined, Visit 1 should take place within 7 days of the Screening Visit

Visit 4: 4 weeks post-randomization

Second dose titration:

If tolerating current dose (SBP > 90 mmHg, Cr ≤ 2.0 mg/dL, and no symptoms of hypotension) then double dose.

- Maximum dose LCZ696 200 mg po BID or valsartan 160 mg po BID (2 active and 2 placebo tablets po BID)

If not tolerating dose, reduce to previously tolerated dose

Assessments: interim history, review of medications, physical examination, KCCQ, routine laboratory testing, core laboratory testing (BNP, NT-proBNP and Cystatin C), and AE monitoring

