12.2 Follow-up Evaluations

Study Visit 3 (Dose Titration / 2 weeks post-randomization +/- 3 days)

At this visit, two weeks after randomization, upward dose titration will occur among subjects tolerating their current dose (SBP > 90 mmHg, Cr ≤ 2.0 mg/dL, and no symptoms of

hypotension). This will consist of doubling the dose up to a maximum dose LCZ696 200 mg po BID or valsartan 160 mg po BID. For those not tolerating the current dose of study drug, the dose will be down-titrated to the previous tolerated dose.

Assessments at this visit include:

- Interim history
- Review of medications
- Physical examination with NYHA class assessment
- Routine laboratory testing (creatinine, BUN, electrolytes – see visit 0 for labs to be collected)
- Core laboratory testing (BNP, NT-proBNP)
- Adverse event monitoring.

Study Visit 4 (Dose Titration / 4 weeks post-randomization +/- 3 days)

At this visit, two weeks after the prior dose titration visit and four weeks after randomization, further dose titration will occur among subjects tolerating their current dose (SBP > 90 mmHg, Cr ≤ 2.0 mg/dL, and no symptoms of hypotension). This will consist of doubling the dose up to a maximum dose LCZ696 200 mg po BID or valsartan 160 mg po BID. For those not tolerating the current dose of study drug, the dose will be down-titrated to the previous tolerated dose.

Assessments at this visit include:

- Interim history
- Review of medications
- Physical examination with NYHA class assessment
- Routine laboratory testing (creatinine, BUN, electrolytes – see visit 0 for labs to be collected)
- Core laboratory testing (Cystatin C, BNP, NT-proBNP)
- KCCQ questionnaire
- Adherence and tolerance assessment
- Adverse event monitoring.

Study Visit 5 (8 weeks after randomization +/- 5 days)

Subjects will continue taking study drug at the highest tolerated dose. If the study drug has not yet been titrated to the maximal dose, or if the dose of study drug was previously down-titrated, it may be up-titrated, at the physician's discretion. If there are any concerns regarding tolerability, the dose may be down-titrated per investigator discretion.

Assessments at this visit include:

- Interim history
- Review of medications
- Routine laboratory testing (creatinine, BUN, electrolytes – see visit 0 for labs to be collected)
- Core laboratory testing (Cystatin C, BNP, NT-proBNP)
- Adherence and tolerance assessment
- Adverse event monitoring

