21 APPENDICES

21.1 Appendix A - Schedule of Assessments

Visit number	0	1	2	3	4	5	6	7	8	9	10	11	
Time of Visit	Enrollment	Run-in*	1 st dose	Dose titration (2 weeks)	Dose titration (4 weeks)	8 weeks	10 weeks	12 weeks	16 weeks	20 weeks	24 weeks	26 weeks	Unscheduled Visit for dose adjustment
Inclusion/Exclusion criteria	x		x										
Information & Informed consent	x												
Physical examination	x	x	x	x	x			x			x		x
KCCQ questionnaire	x				x			x			x		
Dispense study medication		x ¹	x	x	x	x		x			x		x
Laboratory test (routine)+	X [^]	x	x	x	x	x		x			x		x
Laboratory test (core)			x ²	x ³	x ²	x ²		x ²			x ²		
Adverse events		x	x ⁴	x	x	x	x	x	x	x	x		x
Telephone follow-up							x		x	x			
Telephone Safety Assessment												x	

* The Screening visit and Visit 1 may be combined at the investigator's discretion for subjects who are stable and for whom lab results have been reviewed as long as the investigator ensures the 1st dose of LCZ696 \geq 36 hours after last ACEI dose (if applicable). If not combined, Visit 1 should take place within 7 days of the Screening Visit

+ Local lab tests include the following: Sodium, Potassium, Chloride, CO₂/Bicarbonate, Total Calcium, Magnesium, BUN, Creatinine

[^] For Screening/Study Visit 0 only - Standard of care labs are acceptable, using results within 24 hours prior for hospitalized patients and within 7 days prior for outpatients.

¹ Open-label LCZ696 (50 mg po BID) during run-in phase

² BNP, core and Cystatin C

³ BNP and NT-proBNP only

⁴ Run-in failure patients should be contacted approximately 2 weeks after their last dose of study drug.

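### The dose-doubling rule at Visits 3 and 4 has no potassium condition, so read literally it directs doubling in a patient with moderate or severe hyperkalemia

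*Protocol*

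**What the plan says.** The doubling rule appears in four places in the protocol, each time with the same three conditions.

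- Section 8, Visit 4: "If tolerating current dose (SBP > 90 mmHg, Cr ≤ 2.0 mg/dL, and no symptoms of hypotension) then double dose".
- Section 7.3: beyond a systolic pressure above 90 mmHg, the criteria are "changes in renal function (maximum serum creatinine of 2.0 mg/dL), and the absence of symptoms of hypotension".
- Section 10.4, two weeks after randomization: "upward dose titration will occur among subjects tolerating their current dose (SBP > 90 mmHg, creatinine (Cr", followed by the 2.0 mg/dL limit and the hypotension condition. The week 4 rule is the same.
- Section 12.2, Visit 4: "further dose titration will occur among subjects tolerating their current dose (SBP > 90 mmHg, Cr ≤ 2.0 mg/dL, and no symptoms of hypotension". Visit 3 has the same conditions.

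SAP Section 1.2 repeats doubling every two weeks and adds no criteria.

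Potassium is measured at both visits. Section 12.2 lists "Routine laboratory testing (creatinine, BUN, electrolytes" at Visits 3 and 4, and the Appendix A footnote specifies "Local lab tests include the following: Sodium, Potassium, Chloride" among the analytes, with creatinine on the same panel.

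Elsewhere, potassium above 5.5 mmol/L bars entry (Section 9.3). Hyperkalemia is a tolerability measure, moderate at ≥ 5.5 and severe at ≥ 6 mmol/L (Section 13.2). It is also an event of interest from 5.5 mEq/L (Section 15.9). No section gives a potassium value at which study drug is withheld, reduced or stopped.

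**The concern.** Both arms receive a renin-angiotensin blocker, and the protocol expects hyperkalemia with each. Section 11.6 names it among the common reactions to valsartan and among the reactions seen in at least 5% with LCZ696. Entry is allowed down to an eGFR of 20 mL/min/1.73 m².

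The protocol treats blood pressure, renal function and potassium as a set of three hazards in its exclusions and again in its tolerability endpoints. The titration rule keeps the first two and leaves out the third, without giving a reason. A potassium of 5.8 mmol/L would keep a patient out of the trial, yet nothing written bars doubling the dose at that value two or four weeks later. What is at stake is the safety of individual patients during titration.

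**Working it through.** No figure in the plan needs reproducing. The check has three parts.

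**1. Does a hyperkalemic patient meet the written rule?** Take a patient below target dose at Visit 3 or 4 with illustrative values: systolic pressure 100 mmHg, creatinine 1.5 mg/dL, no symptoms of hypotension, potassium 6.2 mmol/L.

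- Pressure: 100 > 90, met.
- Creatinine: 1.5 ≤ 2.0, met.
- Symptoms: none, met.
- Potassium: no condition to test.

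Every written condition is met, so the text calls for doubling. By Section 13.2 the same potassium is severe (6.2 ≥ 6).

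**2. Who faces the decision?** The targets are LCZ696 200 mg and valsartan 160 mg BID (Section 7.3).

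- Start at 50/40 mg: 50/200 = 40/160 = 25% of target, so two doublings, at Visits 3 and 4.
- Start at 100/80 mg: 100/200 = 80/160 = 50% of target, so one doubling, at Visit 3, or at Visit 4 if deferred.

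Nobody starts at target, so every patient still on drug and not yet at target faces the rule at Visit 3, and again at Visit 4 if still below target. The run-in dose is also 50 mg, 25% of target. The Visit 2 eligibility and laboratory recheck therefore follows a planned 3 to 7 days at one quarter of the target dose and says little about potassium after doubling.

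**3. How long until the next scheduled potassium?** From the windows in Section 12.2:

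- Visit 3: day 14 ± 3, so days 11 to 17.
- Visit 4: day 28 ± 3, so days 25 to 31.
- Visit 5: day 56 ± 5, so days 51 to 61.

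After a Visit 3 doubling: nominal 28 − 14 = 14 days; shortest 25 − 17 = 8; longest 31 − 11 = 20.

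After a Visit 4 doubling: nominal 56 − 28 = 28 days; shortest 51 − 31 = 20; longest 61 − 25 = 36. No contact is scheduled in between, since the first telephone visit is at week 10.

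The documents do not say how many patients had potassium ≥ 5.5 or ≥ 6 mmol/L at these visits, and no estimate is made.

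**The case against.** The best defense is that the operative word is *tolerating*. Section 13.2 lists hyperkalemia under tolerability, and patients who do not tolerate their dose are to be down-titrated. On that reading a patient at 6.2 mmol/L is reduced, not doubled. Section 7.3 also calls a pressure above 90 mmHg required for up-titration, which is the language of a necessary condition and not of an automatic trigger.

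Other provisions point the same way:

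- Section 15.5 foresees laboratory abnormalities that lead to interruption or discontinuation of drug.
- Section 15.10 foresees events that need a dose change and gives them an eCRF page.
- Section 12.2 allows unscheduled visits for possible dose changes, with electrolytes measured.
- Visit 4 includes an "Adherence and tolerance assessment".
- Appendix A repeats "Inclusion/Exclusion criteria" at Visit 2.

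Much of this stands. A reader might infer that investigators were obliged to double against an abnormal potassium and had no way out. The documents do not support that: the wider reading is open, and the protocol plainly expects doses to be changed on clinical grounds. A reader might also infer that patients went 20 to 36 days with no potassium check. That interval counts scheduled tests only.

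The defense does not supply the missing condition. In Sections 8, 10.4 and 12.2 the parenthesis spells out tolerance with three items, and potassium is not one of them. Sections 15.5 and 15.10 say how events are recorded, not when to act. The tolerance assessment is listed at Visit 4 but not at Visit 3. Explicit discretion over tolerability is written for the starting dose (Section 10.4) and for Visits 5 and 7 (Section 12.2), but not for the two visits where doubling is directed. A careful clinician would probably withhold the increase, but would be departing from the literal rule, and about 40 centers could each choose a different cut-off.

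**Conclusion.** The point holds as a gap in a written dosing rule. Four protocol sections omit potassium from the doubling criteria, and on the literal reading a patient with moderate or severe hyperkalemia qualifies for a doubled dose. The backstops are real but partial, and none carries a potassium value.

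The number of patients exposed is unknown. The time at the raised dose before the next scheduled potassium is nominally 14 days after Visit 3 (8 to 20) and 28 days after Visit 4 (20 to 36), assuming visits within window and no unscheduled test.

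A reader might go further and infer a distorted treatment comparison or actual harm to patients. Neither follows. The rule is the same in both blinded arms, and the documents give no potassium results by arm or by visit. This is a patient-safety point only.

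Its practical value now is limited. SAP Section 3 reports 365 patients randomized and Section 14 describes the interim analysis in the past tense, so few or none may still be before week 4.

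**What to change.** 1. Add potassium < 5.5 mmol/L to the doubling criteria in Sections 7.3, 8, 10.4 and 12.2 (Visits 3 and 4). Between 5.5 and < 6 mmol/L the dose then stays where it is.
2. State that potassium ≥ 6 mmol/L counts as not tolerating, so that the existing down-titration rule applies, and that drug is held if the patient is already on the lowest dose (50/40 mg).
3. When doubling is withheld or the dose is cut for potassium, recheck it at the unscheduled visit that Section 12.2 already provides. Without this, such a patient could still wait until the next scheduled panel.

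The cut-offs are the protocol's own categories; the actions attached to them are a proposal and have no source in the documents. The < 5.5 limit also bars doubling at exactly 5.5 mmol/L, a value that was allowed at entry. Visits 5 and 7 need no change, because dose changes there are already left to the physician.

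The cost is wording in four sections and a few extra local panels. No new test is needed at Visits 3 and 4, because potassium comes with the creatinine that the rule already uses. The downside is that some patients will reach a lower dose.
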